#### 4.5.3. Benefits

The American Academy of Pediatrics Committee on Fetus and Newborn supports a shorter hospital length of stay, as it benefits the family and infant, allowing for less separation as well as possibly decreasing the risk for hospital-acquired infections. However, due to the uncertainty in the timing of resolution of apneic episodes in preterm infants, it is challenging for neonatologists to know when to discontinue caffeine and discharge patients home. A common problem is that even after infants have fulfilled other criteria for discharge, such as thermoregulation and full oral feeds, apnea may still be present and can prolong hospitalization, as was illustrated in a study where 15.8% (222/1403) of infants at 34 weeks' PMA continued to have recurrent apneic episodes as the only reason for remaining hospitalized.

A potential benefit of trial participation and randomization to the Caffeine arm is that there may be fewer episodes of apneas in the NICU and the infant may be able to be discharged home earlier than those infants who receive placebo. This decreases the time that parents are stressed with a hospitalized infant as well as potentially decreasing the risk of intra-hospital acquired infections. In addition, with the administration of caffeine at home, there is the possibility of reducing apneic episodes that could lead to readmissions to the hospital or require sick visits to the health care provider, urgent care, or emergency room with further evaluation with x-rays and blood sampling. Also, the Caffeine for Apnea trial showed the benefits of caffeine use as it relates to patent ductus arteriosus, with a reduction in both medical (29.3% vs. 38.1%) and surgical (4.5% vs. 12.6%) treatment.

Another potential benefit of the proposed trial would be the reduction of intermittent desaturation events in the infants continuing caffeine treatment. Intermittent desaturations, regardless of apneic episodes, may be related to neurodevelopmental impairment in premature infants as well as the development of retinopathy of prematurity. A recent small randomized controlled trial compared the use of prolonged caffeine citrate versus no caffeine in infants between 34 and 37 weeks GA to reduce intermittent desaturations. Infants of 35 weeks and 36 weeks GA in the caffeine group had a reduction in episodes of desaturations below 90% by 52% (95% CI, -70% to -22%) and 46% respectively (95% CI, -65% to -11%) but there was no reduction in desaturations from 37 weeks and beyond.

This trial is testing caffeine treatment, which is used in NICUs throughout the world, with the main difference being the timing of discontinuation of treatment. As such, the subjects may receive no direct benefit from participating in this study.

Infants receiving one treatment may have improved outcomes over those seen in the other treatment group. We do not know which treatment group will or will not show improvement and it is possible that the outcomes will be the same for the two treatment groups.

## SECTION 5. METHODS

---

### 5.1. STUDY POPULATION

#### 5.1.1 Inclusion Criteria

Inborn and outborn infants of  $29^{0/7}$  to  $33^{6/7}$  weeks GA at birth and admitted to hospitals of the National Institute of Child Health and Human Development Neonatal Research Network  $\leq 72$  hours of age will be eligible if they meet all of the following inclusion criteria at time of enrollment:

- a.  $33^{0/7}$  -  $35^{6/7}$  weeks PMA at the time of randomization
- b. Receiving caffeine with plan to discontinue treatment or just discontinued caffeine treatment
- c. Receiving full feeds (defined by a volume of  $\geq 120$  ml/kg/day) by oral and/or tube feeding
- d. Ability to start study medication within 72 hours after stopping caffeine,

#### 5.1.2 Exclusion Criteria

Any of the following criteria will exclude an infant from the trial:

- a. On respiratory therapy (oxygen more than room air equivalent for high altitude sites, nasal cannula, continuous positive pressure ventilation, and/or mechanical ventilation)
- b. Infants who would otherwise be discharged home on apnea monitor due to underlying disease or family history, including history of a sibling with sudden infant death syndrome
- c. Parental request for apnea monitor
- d. Congenital heart disease other than atrial septal defect, ventricular septal defect, or patent ductus arteriosus
- e. Neuromuscular conditions affecting respiration
- f. Major congenital malformations and/or genetic disorders
- g. Plans to transfer to a non NRN site before discharge
- h. Unable to obtain parental or guardian consent

### 5.2. DETAILED STUDY PROCEDURES

#### 5.2.1. Screening and Consent

Initially, the research nurses, coordinators, and physicians will identify all infants born between  $29^{0/7}$  and  $33^{6/7}$  GA at birth. Consent can be obtained at any time. Evaluation for enrollment in the trial will be done once there are plans to discontinue caffeine treatment and the infant is between  $33^{0/7}$  and  $35^{6/7}$  weeks PMA (inclusive). Parents or a legal guardian of the infant who meets all the inclusion criteria and does not meet any of the exclusion criteria will be approached by the research nurse, coordinator, and/or physician for written informed consent. Infants who are deemed to require apnea monitoring at home after enrollment has occurred will be allowed its use and this will be noted on the Follow-up form.

### **5.2.2. Randomization Procedures**

When the attending neonatologist has discontinued clinical caffeine on an eligible and consented infant that is  $33^{0/7}$  -  $35^{6/7}$  weeks PMA, the infant can be randomized if it is possible to start study medication within 72 hours after stopping caffeine.

Infants will be randomized 1:1 using a stratified permuted block design with a centralized procedure. Infants will be stratified by study center into two GA groups; infants born at 29 to 30  $6/7$  weeks GA and 31 to  $33^{6/7}$  weeks GA. Randomization will occur through the Data Coordinating Center of RTI International (Research Triangle Park, North Carolina). Treatment allocation will be revealed only to the research pharmacy staff, who will prepare either caffeine citrate at 10 mg/kg (base of 5 mg/kg) or an equivalent volume of placebo to be administered once a day. The dosage will be based on the weight closest to randomization and then adjusted weekly for weight. Because both caffeine and placebo are colorless, they are indistinguishable and, therefore, blinding will be accomplished for all care providers and research staff.

The oral delivery should begin as soon as clinically possible.

Randomization of twins and higher order multiples (when eligible) will be done separately.

### **5.2.3. In-hospital Procedures**

Study subjects are infants in the NICU at one of the principal or associated sites of the NRN. Once the attending physician has discontinued caffeine therapy, the infant will be randomized as described in section 5.2.2. The research pharmacist will be notified of enrollment and the infant will receive a once-a-day dose of caffeine citrate at 10 mg/kg/dose (5 mg/kg caffeine base) as part of the treatment group or receive placebo at the same volume and time every 24 hrs and not given less than 12 hours apart. The doses will be weight adjusted on a weekly basis. If the infant is later put NPO, the oral caffeine citrate or placebo will be held until feeding resumes and at the discretion of the attending neonatologist.

In-hospital apnea and bradycardia events will be monitored using individual study site monitor devices. There are no universal definitions for apnea and bradycardia and therefore, diagnoses of these will be left at the discretion of each hospital group of neonatologists (pre-specified) and the neonatal team caring for the infant. The data on apnea and bradycardia will be used to determine physiologic maturity and for the local decision about discharging the babies home. The definitions of apnea and bradycardia will be decided locally. However, for the purposes of this study, significant apnea/bradycardia will be defined as apnea/bradycardia events receiving treatment. Treatment is defined as ordered by the attending physician (e.g. re-starting caffeine, not just stimulation for example). Using local definitions will increase generalizability and interfere less with local decision making.

Data will be collected from the infant's electronic or physical chart. The number of infants who receive CPAP, mechanical ventilation, and/or open label caffeine, other methylxanthine or doxapram for the treatment of apnea/bradycardia after randomization will be noted for the study.

The protocol will allow for individual study site centers to use their own discharge criteria, but for the purposes of the definition of secondary outcome of the trial, infants must have reached physiologic maturity, which includes a) out of an incubator for at least 48 hours, b) oral feeding at volume of at least 140 ml/kg/day or growing on less than 140 ml/kg/day for at least 48 hours, and be apnea-free for at least 5 consecutive days. Infants who are still in the hospital at 44 weeks PMA will have the study medication (caffeine/placebo) discontinued. Analysis will be done by intention to treat. If an infant is discharged before meeting the definition of physiologic maturity, it will be noted for analysis at the conclusion of the trial. The weight within 48 hours of discharge will be used for the caffeine/placebo home administration. The dose will not be adjusted for weight gain after discharge. The practice of discharging infants home on open-label caffeine will not be a part of the trial. However, should it occur, it will be noted as a protocol deviation and will be noted for subsequent analysis.

Prior to discharge, a research nurse, physician, or pharmacist will educate the parents on storage and administration of the medication to the infant. Other instructions to the parents include preparation of daily dose and if a dose is missed, it may be given at any time on that day if the dose can be given at least 12 hours before the next day's dose is due. If it was not given at all, the parents will be instructed to discard the entire vial that was missed and record it on the medication form. If an infant spits or vomits after a dose is given, another dose should not be given on the same day. Follow-up forms (Medication and Follow up Forms) will be supplied to allow the parents to keep track of daily medication administration and missed doses. The parent will be given a stamped envelope to return the forms to the NRN research coordinator at the end of the 8 weeks. If the study site allows for the use of a gift card, it will be mailed to the parent or guardian when the documents are returned to the research coordinator. The gift card will encourage the family member to return the follow up documents at the end of the 8-week follow up period. Because it will be supplied at the end of the study period, it will have no consequences to the enrollment or treatment of the infant. In addition, the gift card does not constitute payment to the family member for any service provided as part of the trial.

Of note, infants who are deemed to require apnea monitoring at home after enrollment will be allowed its use and this will be noted on a follow-up form. Data from the home monitor recordings will not be used in the trial.

The NRN research coordinator and staff will obtain maternal demographics data including age, race, education, marital status, and parity. In addition, infant data will also be recorded, including weight at birth, randomization, and status; length/head circumference at birth and status; date of status; date of last apnea episode recorded after randomization; use of CPAP or mechanical ventilation; date of last NPO episode lasting >24 hours as well as the number of episodes of NPO >24 hours following randomization; date of last orogastric or nasogastric feed; date of last day in incubator; dates of initiation and termination of open label caffeine therapy; and information related to side effects and adverse events.

#### **5.2.4. Post-hospital Procedures**

Following discharge, the research team will contact the family within 72 hours after discharge, once a week for the first 4 weeks, and biweekly during the weeks 5 to 8 after discharge to ensure the study medication is being administered adequately and to gather information on doctor or hospital visits.

Parents will be given a Health Care Provider Letter. A copy will also be sent directly to the Health Care Provider's office. The letter will clearly describe the trial goals and procedures, the dose of the study medication, and PI contact information.

## SECTION 6. ANALYTICAL PLAN

---

### 6.1. SAMPLE SIZE AND AVAILABILITY

To obtain a two-day difference in primary outcome of days from randomization to discharge, from 14 days to 12 days, with a power set at 90%, a significance of 0.05, and a 5% attrition, the trial would require 587 infants per group (intervention and placebo) for a total of 1174 infants, assuming a two-tailed non parametric test comparing median LOS in the two groups. With a power set at 80%, under the same assumptions and significance, the trial would require 439 infants per group for a total of 878 infants. The minimum required sample size for this trial will be 878 (439 in each treatment group), but enrollment will continue until either the presently-acquired supply of study drug is exhausted or expires in approximately August 2023 (accounting for full in-hospital and post-discharge follow-up), whichever comes first. There are approximately 3000 infants born between  $29^{0/7}$  and  $33^{6/7}$  weeks gestation per year in the NRN. A review of 100 infants in the NICU at one of the largest centers in the NRN showed that 37% of infants within this cohort were treated with a methylxanthine. This is similar to NRN data showing that approximately 1000 (one-third) of infants receive caffeine therapy.

Effect Size (days)	Significance	Power (%)	Attrition (%)	Sample Size
14 to 10	0.05	80	5	226
14 to 10	0.05	90	5	302
14 to 12	0.05	80	5	878
14 to 12	0.05	90	5	1174

### 6.2. STATISTICAL ANALYSIS PLAN

The primary analysis will compare number of days of hospitalization from randomization to discharge, death, transfer or 48 weeks PMA, whichever occurs first between the intervention and control groups using median regression controlling for study center and GA group (the two stratification factors for this trial). Likewise, the treatment effect for the secondary outcomes (number of days to physiologic maturity after randomization, number of readmissions and number of sick visits) will be compared using either median regression or a Poisson regression model controlling for study center and GA group.

Secondary analyses will evaluate whether other models better fit the distributions for these outcomes (for example, survival analysis models for the primary outcome and negative binomial or log linear models for the secondary outcomes).

We will examine treatment heterogeneity for the primary outcome by adding interaction terms between treatment and study center, as well as treatment and GA group. If any of these interaction terms are close to statistical significance ( $p<0.1$ ), for treatment heterogeneity by study center, we will attempt to identify centers where the treatment effect may be different (although the statistical power available to conduct such analyses will be fairly limited). If there is

indication of treatment heterogeneity by GA group, we will conduct stratified analyses by GA group to quantify the treatment effect separately by GA group.

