### 4.1. PRIMARY OUTCOME

The primary outcome of the study will be the number of days of hospitalization from randomization to discharge up to 48 weeks PMA, with censoring at time of transfer or death.

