## 5 ANALYSIS POPULATIONS

## **Intention-to-Treat Population (ITT)**

The intention-to-treat population will comprise of all randomized participants who have at least one efficacy measurement. Participants who receive study drug but do not complete the study will be used in all analyses for which data are available. Participants who are withdrawn for further follow-up will be treated as lost to follow-up at the time that consent was withdrawn, and data will be used up to the time of study withdrawal (unless parents/guardians expressly forbid use of any collected data).

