## 9.2 Efficacy Variables

Primary and secondary efficacy variables are described in the table below.

| Variable                               | Type  | Definition   |  |
|--|-------|--|--|
| Primary Outcome                        |       |  |  |
| Number of days of hospitalization      | Count | The number of days between randomization and hospital discharge. This outcome is censored at 48 weeks PMA and at time of transfer or death   |  |
| Secondary Outcomes                     |       |  |  |
| Number of days to physiologic maturity | Count | Physiologic maturity is defined:  i. Temperature: out of the incubator for at least 48 hours with normal body temperature  ii. Feeding: oral feeding at a volume of at least 140 ml/kg for 48 hours or growing on less than 140 ml/kg/day for at least 48 hours  iii. Respiratory: apnea-free for at least 5 consecutive days  This outcome is censored at 48 weeks PMA. |  |

| Variable  | Type       | Definition  |
|---|------------|---|
| Number of days to physiologic maturity - Temperature                        | Count      | Physiologic maturity is defined:  i. Temperature: out of the incubator for at least 48 hours with normal body temperature  This outcome is censored at 48 weeks PMA.  |
| Number of days to
physiologic maturity –
Feeding                      | Count      | Physiologic maturity is defined:  i. Feeding: oral feeding at a volume of at least 140 ml/kg for 48 hours or growing on less than 140 ml/kg/day for at least 48 hours  This outcome is censored at 48 weeks PMA.            |
| Number of days to
physiologic maturity -
Respiratory                  | Count      | Physiologic maturity is defined:  i. Respiratory: apnea-free for at least 5 consecutive days This outcome is censored at 48 weeks PMA.  |
| Post-menstrual age at discharge   | Continuous | The post-menstrual age of the infant at discharge censored at 48 weeks PMA and at time of transfer or death   |
| Number of all-cause
readmissions within first 4
weeks post-discharge  | Count      | Number of hospital readmissions including apneic events and apparent life-threatening events during first 4 weeks following hospital discharge. The outcome is censored at 48 weeks PMA.                                    |

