## 9.3 Primary Analysis Methods

For the primary analysis, the number of days of hospitalization between randomization and discharge will be compared between the caffeine citrate and placebo groups using either median or robust Poisson regression models. The model will include a fixed effect for treatment group. The model will also be adjusted for the design effect of stratification by site and gestational age. Estimates, p-values and 95% confidence intervals will be presented for treatment group comparisons. In an intent-to-treat fashion, all data will be included in the primary model based on their randomized treatment, regardless of the treatment administered to the patient. If there are important baseline characteristics that differ between randomized treatment groups by chance, additional sensitivity analyses may be conducted to evaluate the impact of those imbalances.

We will examine treatment heterogeneity for the primary outcome by adding interaction terms between treatment and study center, as well as treatment and gestational age group, and following NIH guidelines, treatment and sex. If any of these interaction terms are close to statistical significance (p<0.1), for treatment heterogeneity by study center, we will attempt to identify centers where the treatment effect may be different (although the statistical power available to conduct such analyses will be fairly limited). If there is indication of treatment heterogeneity by GA group and/or sex, we will conduct stratified analyses by GA group and/or sex to quantify the treatment effect separately by GA group/sex.

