## 10.2 Safety Variables

Safety outcome variables are described in the table below.

| Variable   | Туре                       | Definition  |
|--|----------------------------|---|
| Safety Outcomes  |                            |   |
| Weight gain from randomization until status  | Continuous/
Categorical | Change in weight between randomization and in-hospital status. Outcome is censored at 48 weeks PMA and time of transfer or death. May also be assessed using percentiles.   |
| Number of days after
randomization until status
that infant had at least two
consecutive heart rates >200
documented at least 3 hours
apart | Count                      | Number of days between randomization and status with at least 2 consecutive heart rates > 200 bpm at least 3 hours apart. Outcome excludes when infant was crying.  |
| Treatment for high blood pressure initiated after randomization until status   | Categorical                | Presence of treatment for high blood pressure that was started between randomization and status.  |
| Number of episodes between randomization and status that infant was placed NPO for ≥ 24 hours  | Count                      | Number of days between randomization and status in which infant was placed NPO for at least 24 hours  |
| Use of anti-reflux medications between randomization and status  | Categorical                | Presence of use of anti-reflux medication that were started between randomization and status.   |
| Number of days of
significant apnea/bradycardia
between randomization and
status  | Count                      | Number of days between randomization and status with infant showing significant apnea/bradycardia. Significant apnea/bradycardia documented by infant receiving open label caffeine, doxapram, other methylxanthines, CPAP or ventilatory support for apnea/bradycardia |

| Variable  | Type        | Definition   |
|---|-------------|--|
| Presence of documented and treated arrhythmias between randomization and status | Categorical | Presence of treated arrhythmias between randomization and status. Outcome excludes arrhythmias due to tachycardia or bradycardia     |
| Onset of documented seizures between randomization and status                   | Categorical | Presence of documented seizures between randomization and status. Documented seizures are defined by treating with anti-convulsants. |

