#### 13 CHANGES TO THE ANALYSES PLANNED IN THE PROTOCOL

None at this time. Additional analyses motivated by observations in the final outcome data may be conducted, but these will be clearly identified as post-hoc analyses in any publication and will not be specifically addressed via updates to the SAP.

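### The primary outcome is defined as censored at transfer or death, but no censored estimator is named for the primary analysis, so an early exit can be scored as a short completed stay

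*Protocol*

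**What the plan says.** **Outcome definition.** Protocol 4.1 and SAP 3.2.1 count days from randomization to discharge up to 48 weeks PMA, "with censoring at time of transfer or death". The table in SAP 9.2 repeats this and adds the age limit: "This outcome is censored at 48 weeks PMA and at time of transfer or death".

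**Primary analysis.** Protocol 6.2 compares days of hospitalization "from randomization to discharge, death, transfer or 48 weeks PMA, whichever occurs first between the intervention and control groups using median regression", adjusted for center and GA group. SAP 9.3 compares days between randomization and discharge "using either median or robust Poisson regression models", with all infants kept in their randomized arm.

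**Related text.**
- SAP 7.3 expects no missing primary outcome data and gives no rule for deaths or transfers, although SAP 4.7 foresees both.
- SAP 5 says of consent withdrawals that "data will be used up to the time of study withdrawal".
- Survival models appear in Protocol 6.2 and SAP 9.4 only among secondary analyses of model fit. SAP 15 lists a survival plot.
- SAP 13, on changes from the protocol, reads: "None at this time. Additional analyses motivated by observations in the final outcome data may be conducted".
- The interim efficacy looks use the same analysis: Protocol 6.3.3 points to section 6.2, and SAP 7.4 points to SAP section 9.

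**The concern.** If an outcome is censored at death or transfer, an infant who leaves on day 3 tells the analysis only that the stay would have exceeded 3 days. If the count simply ends at the first of four events and goes into a median or Poisson regression, the same infant has a 3-day stay. Because a shorter stay is the hoped-for result, a death or early transfer then counts as a success.

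The primary estimate, its p-value and the interim stopping p-values would all carry this scoring. The SAP also leaves the primary model open. Median regression targets a median, which is what the sample size is based on. Robust Poisson regression targets a mean, and Protocol 6.2 does not name it for the primary outcome. Neither model, as described, has a place for censoring.

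**Working it through.** **1. The texts side by side**

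| Place | Where the count ends | Role of transfer or death | Estimator |
|---|---|---|---|
| Protocol 4.1, SAP 3.2.1 | Discharge, up to 48 weeks PMA | Censoring | None named |
| SAP 9.2 | Discharge | Censoring, as is 48 weeks PMA | None named |
| Protocol 6.2 | First of discharge, death, transfer, 48 weeks PMA | End of the count | Median regression |
| SAP 9.3 | Discharge | Not stated | Median or robust Poisson |
| Protocol 6.2, SAP 9.4 (secondary) | Not stated | Not stated | Survival models, as an example |

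No row combines the censored definition with a censored estimator for the primary analysis.

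**2. The plan's own figure, as background**

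The inputs are 14 to 12 days, two-sided 0.05, 80% power and 5% attrition (Protocol 6.1, SAP 6). The documents give no SD, so one was back-solved: 10.3 days. Then n = 2 × 10.3² × (1.960 + 0.842)² / 2² = 417 per group after rounding up, and 417 / 0.95 = 439, or 878 in total as stated. The 90% row gives 1176 against the stated 1174. This point does not dispute the sample size.

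**3. Assumptions for the size of the effect**

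The documents give no death or transfer rate. The 5% attrition figure is not an exit rate. Assumed here: lognormal stay, median 14 days, log-SD 0.6, 439 per arm. The SD this implies is 14 × exp(0.18) × √(exp(0.36) − 1) = 11.0 days, close to the back-solved 10.3. Center and GA group were not modelled.

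**4. Precision**

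- Density at the median: f = 1 / (14 × 0.6 × √(2π)) = 0.0475.
- SE of the median difference: √(2/439) × 0.5 / 0.0475 = 0.711 day.
- Nominal significance: 1.96 × 0.711 = 1.39 days.

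**5. Shift per point of excess exits in one arm, exits scored as stays**

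- Random infants, all leaving before day 14: 0.005 / 0.0475 = 0.105 day (simulated 0.104).
- Infants who would have stayed beyond 14 days, all leaving before day 14: 0.01 / 0.0475 = 0.211 day (simulated 0.207).
- Exit spread evenly over the infant's own stay: 0.069 day (random infants) and 0.137 day (longer-stay infants), by simulation.

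The range is about 0.07 to 0.21 day, or 0.06 to 0.25 for log-SD 0.5 to 0.7, against a 2-day target.

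**6. Excess needed for exits alone to reach 1.39 days**

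At the top of the range, 1.39 / 0.211 = 6.6 points. At the bottom, 1.39 / 0.069 = 20 points if the shift were linear. It grows slightly faster than that: simulation gives 0.93 day at 13 points and 1.45 days at 20, crossing 1.39 at about 19. The range is about 7 to 19 points.

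**7. Two-sided false-positive rate with no true effect (40,000 simulated trials, error about 0.1 point at 5%)**

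| Exits by arm | Rate |
|---|---|
| 1% v 1% | about 5% |
| 2% v 1% | 5.2% to 5.5% |
| 5% v 3% | 5.4% to 6.0% |
| 3% v 1% | 5.5% to 7.7% |
| 5% v 1%, spread over the stay | 7% to 10% |

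**8. With a true 2.0-day benefit (14 v 12 days; lognormal or gamma stay)**

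| Exits, placebo / caffeine | Exits scored as stays | Exits censored |
|---|---|---|
| 5% / 5% | 1.93 to 1.94 | 2.02 to 2.03 |
| 5% / 2% | 1.73 to 1.76 | 2.11 to 2.17 |
| 2% / 5% | 2.15 to 2.19 | 1.87 to 1.92 |

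The distortion can favour either arm. Censoring does not recover 2.0 exactly, because these simulated exits are related to the stay.

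**The case against.** **The two rules may be compatible.** The first of discharge, death, transfer or 48 weeks PMA is also how observed time is defined in a censored analysis, with discharge as the only event. Censored median regression is itself a median regression. On that reading only the estimator's name is missing. This stands as a possibility. It is made less likely by the robust Poisson option and by survival models being offered only as secondary alternatives, and the text does not settle it.

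**Censoring may be loose wording.** SAP 10.2 says of weight gain: "Outcome is censored at 48 weeks PMA and time of transfer or death". That variable has no event time, so the word there can only mean that measurement stops. If the same is meant for the primary outcome, the definitions need rewording, because a reader would expect a censored analysis.

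**Stronger readings that the documents do not support.** A reader might infer that an early exit is scored as a short stay whatever the wording means. That is not so: under censoring in its statistical sense a day-3 transfer contributes only a stay longer than 3 days. A reader might also infer that SAP 13 makes the rule in Protocol 6.2 prevail. A statement that there are no changes does not rank that section above the definition in SAP 9.2.

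**Safeguards.** Allocation is masked. Infants on respiratory therapy are excluded, as are those with "Plans to transfer to a non NRN site before discharge". Mortality and disposition are reported, and a time-to-discharge view is planned. A large imbalance would be seen, but the primary estimate would not reflect it. The exclusion does not cover unplanned or within-network transfers.

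**Censoring is no cure.** Death competes with discharge, and censoring it treats a dead infant as one who could still have gone home. This stands, and it is why sensitivity analyses are needed.

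**Conclusion.** The inconsistency is real and concerns the primary outcome. The definition calls for censoring, no censored estimator is named for the primary analysis, and the SAP leaves two models open while declaring no change from the protocol. Applied as written, the analysis scores an early death or transfer as a completed short stay.

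The likely effect is small. Equal exit rates leave the false-positive rate at about 5%, and modest imbalance raises it by up to about 1 point (2% v 1% or 5% v 3%). A reader might infer that exits could produce a positive trial by themselves; the 7 to 19 points of excess needed make that implausible in this population. All these sizes rest on assumed exit rates and an assumed lognormal stay, without center or GA effects.

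The sponsor should correct this before unblinding, mainly to have one fixed rule. The open choice of robust Poisson is a related but separate gap and does not make the censoring issue larger.

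**What to change.** Before unblinding, align Protocol 6.2 and SAP 9.2 and 9.3:

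1. **One primary model of time to discharge.** Only discharge is an event. Transfer, consent withdrawal and 48 weeks PMA are censored, and death is censored as the outcome definition states. Censored median regression with treatment, center and GA group is one example, once it is confirmed that it can be fitted with the center effects.
2. **Remove robust Poisson** as an alternative for the primary outcome.
3. **Prespecify two sensitivity analyses:** deaths and transfers kept as not discharged through 48 weeks PMA, and the first-of-four-events analysis of Protocol 6.2.
4. **Report deaths and transfers by arm** beside the primary result.
5. **List the change in SAP 13** and apply the same model at any remaining interim look.

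The sensitivity analyses are needed because censoring reduces but does not remove bias. With 3% exits in one arm and none in the other, simulated bias is −0.20 to −0.59 day when exits are scored as stays (negative meaning a shorter apparent stay in the arm with exits). It is −0.24 to +0.11 day when they are censored, and 0 to +0.34 day when they are held as not discharged. In these scenarios the two sensitivity analyses roughly bracket the true value.

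**Cost.** Reworded text and a little more analysis. No new data are needed: date of status is collected (SAP 4.8) and final study status is tabulated (SAP 15). Intervals widen by about 2% to 3% (SE 0.72 v 0.70 day at 3% exits per arm, 0.73 v 0.71 at 5%).
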